### 8.6.2. Resourcing needs

Not applicable.

### 8.6.3. Timings of Assessment during follow-up

**Table 5 Timing of Cohort Enrollment, Interviews, Medical Records**

	<20 weeks gestation	16-20 weeks gestation*	32-34 weeks gestation	0-6 weeks after delivery	0-12 months after delivery
Contact / Referral	√	√	√		
Enrollment and Consent	√	√	√		
Intake Interview	√	√	√		
Interim Interview I		√			
Interim Interview II			√		
Outcome Interview				√	
Medical Record Release Forms Sent for Signature				√	
Medical Record Review					√

## 8.7. Data analysis

### 8.7.1. Essential analysis

A detailed Data Analysis Plan will be prepared and finalised prior to the conduct of any study analysis or reporting.

*Primary Endpoint:* The primary endpoint will be major structural defects among live born infants. The primary comparison will be between the first-trimester mepolizumab-exposed group and the treated disease cohort.

Secondary comparisons for major birth defects will be conducted with the denominator including all pregnancies ending in live birth, spontaneous abortion, stillbirth or elective termination, excluding lost-to-follow-up, comparing first-trimester mepolizumab-exposed to the treated disease cohort.

Additional secondary comparisons will be made between the first-trimester mepolizumab-exposed group and the treated asthma and non-asthmatic cohort. A tertiary objective of the study is to descriptively compare the rate of major birth defects in the mepolizumab-exposed pregnancies, and control groups to external data from the Centers for Disease Control and Prevention (CDC) Metropolitan Atlanta Congenital Defects Program (MACDP), a population-based birth defects surveillance program ([Centers for Disease Control and Prevention](#), 1998).

*Secondary Endpoints:*

Preterm Delivery: After exclusion of twins or higher order multiples, the rate of pregnancies ending in live birth <37 weeks' gestation will be compared between the mepolizumab group enrolled and exposed anytime in pregnancy prior to 37 weeks' gestation and the treated disease and non-asthmatic cohorts enrolled prior to 37 weeks' gestation.

Small for Gestational Age Infants: After exclusion of twins or higher order multiples, the proportion of pregnancies ending in a live born infant  $\leq 10^{\text{th}}$  centile of birth

weight for gestational age and sex will be compared between the mepolizumab-exposed group and the treated disease and non-asthmatic cohorts.

Spontaneous Abortion: For those women in all three cohorts who enrolled in the study prior to 20 weeks' gestation, the rate of spontaneous abortion accounting for left truncation will be compared between those in the mepolizumab group enrolled and exposed any time in pregnancy prior to 20 weeks' gestation and the treated disease and non-asthmatic cohorts.

Stillbirth: The rate of pregnancies ending in stillbirth will be compared between those in the mepolizumab-exposed group and the treated disease and non-asthmatic cohorts.

*Statistical methods*: Descriptive tables will be prepared for characteristics of each of the cohorts in each interim and final report displaying means and standard deviations, or proportions and percentages.

For the primary endpoint of major structural defects and for the secondary endpoint of small for gestational age infants, crude comparisons will be made using exact methods to develop relative risk estimates and their 95% confidence intervals.

For the secondary endpoints of preterm delivery, spontaneous abortion, and stillbirth, survival methods will be used (Kaplan Meier) to estimate crude rates and confidence intervals accounting for gestational timing of enrollment in the study.

Adjusted analyses producing rates and 95% confidence intervals, where numbers permit, will be conducted for major birth defects and small for gestational age infants using logistic regression. Adjusted analyses producing rates and 95% confidence intervals, for preterm delivery, spontaneous abortion and stillbirth, where numbers permit, will be conducted using Cox Proportional Hazards. A minimum of 30 events in the overall analysis sample is required for adjusted analysis for those outcomes assessed with logistic

regression. A minimum of 20 events in the overall analysis sample is required for adjusted analysis for those outcomes assessed with Cox Proportional Hazards.

Confounders will be considered for each adjusted analysis separately, using the method of change in estimate of the effect of exposure to mepolizumab by 10% or more. If one confounder is identified, direct adjustment will be performed. However, given the expected low frequency of events in a study of this size, if two or more confounders are identified in any given analysis, a propensity score approach for adjustment will be considered.

Appropriateness of models will be assessed graphically and by standard statistical methods

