#### Exclusion Criteria

- Women will not be eligible for Cohort 1 if they first contact the PPD [REDACTED] after prenatal diagnosis of a major birth defect, although data will be collected on these retrospective reports and descriptive information will be included in annual and final study reports.
- Women will not be eligible for Cohort 1 if they have enrolled in the study with a previous pregnancy.

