#### Exclusion Criteria

- Women who have received treatment with mepolizumab but who are not eligible for Cohort 1 will not be eligible for Cohort 2.
- Women will not be eligible for Cohort 2 if they first come in contact with the PPD [REDACTED] after prenatal diagnosis of a major birth defect.
- Women will not be eligible for Cohort 2 who have enrolled in the study with a previous pregnancy.

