### **8.7.2. Exploratory analysis**

Exploratory analyses addressing potential effect modifiers such as Asthma Control Test measures of disease symptom control, and measures of asthma exacerbation will be addressed. In addition, subanalyses based on length and gestational timing as well as dose of exposure to mepolizumab will be performed. Additionally, stratified analyses based on prenatal diagnosis performed prior to enrollment in the study will be conducted for the primary endpoint. The purpose of this analysis is to address the inherent bias in excluding women at the time of enrollment in the cohort study who have already received prenatal diagnosis of a major birth defects, but including women who have already had a normal result or prenatal diagnosis for major birth defects prior to enrollment. Therefore, the planned stratified analysis will compare the birth prevalence of major birth defects among the subset of women enrolled in the cohorts *prior to* prenatal diagnostic testing for fetal structural anomalies, to the birth prevalence of major birth defects among the subset of women enrolled in the cohorts *after* prenatal diagnostic testing for fetal structural anomalies. Subanalyses excluding chromosomal or known genetic anomalies (based on specific defects categorized by expert based on known genetic etiology) will also be conducted.

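### The tertiary comparison with MACDP uses cohort defect rates that entry selection biases downward, and the remedy in 8.7.2 is not extended to it

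*Protocol*

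**What the plan says.** Protocol 8.7.1 (Essential analysis) includes a tertiary objective "to descriptively compare the rate of major birth defects in the mepolizumab-exposed pregnancies, and control groups to external data". The external source is MACDP, described there as "a population-based birth defects surveillance program". The sentence does not restrict the comparison by when women enrolled.

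The exclusion criteria in 8.2 bar a woman from Cohort 1 if her first contact comes "after prenatal diagnosis of a major birth defect, although data will be collected on these retrospective reports". Those reports are described separately and do not enter the cohort rate. Cohorts 2 and 3 carry the same bar, for contact "after prenatal diagnosis of a major birth defect".

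Section 8.7.2 (Exploratory analysis) describes the other half of the filter: the cohorts end up "including women who have already had a normal result or prenatal diagnosis for major birth defects prior to enrollment". Given the exclusions in 8.2, this has to mean women whose earlier testing was normal. The section states the problem plainly: "The purpose of this analysis is to address the inherent bias in excluding women at the time of enrollment in the cohort study". Its remedy is that "stratified analyses based on prenatal diagnosis performed prior to enrollment in the study will be conducted for the primary endpoint", contrasting women enrolled before and after testing for structural anomalies.

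On timing, Table 5 ticks enrolment as late as "32-34 weeks gestation", and 8.5 allows that some women in all three cohorts may enrol after 20 weeks. Section 8.5 also expects exposed women typically to enrol once they know they are pregnant.

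**The concern.** A woman whose defect is found before she contacts the study cannot enter a cohort. A woman with a clear result can. Every late entrant has therefore passed a screen that the reference population has not, and the cohort rate is lower than it would be without that screen.

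Between Cohorts 1 and 2 the filter acts on both sides, so it may largely cancel if enrolment timing relative to testing is similar. Against a population-based reference it acts on one side only. At stake is a safety statement: part or all of a modest increase in defects could be hidden, and a cohort rate near the external rate could be read as more reassuring than it is.

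**Working it through.** The protocol gives no figure for the MACDP comparison, so there is nothing to reproduce. The check asks how far the entry filter alone moves the rate when the drug has no effect.

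**Inputs**
- p = 3%, the prevalence assumed for the asthmatic comparison group under Table 3. It is used only as an illustrative unselected rate; no MACDP rate is given.
- n = 180 exposed live births with completed outcome (Table 3, 90% of 200).
- s = share of otherwise eligible women who first make contact after testing. Not given; assumed 10% to 75%.
- d = share of major defects that such testing detects. Not given; assumed 20% to 70%.

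The formula takes testing before contact to be unrelated to the underlying defect risk.

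**Formula.** The filter removes p·s·d of the women, all of them cases:

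expected cohort rate = p(1 − s·d) / (1 − p·s·d)

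The removed share is small (0.03 × 0.50 × 0.50 = 0.75% of women in the 50%/50% case), so s is close to the share of enrolled women who had a prior normal result.

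**Worked cases**
- s = 10%, d = 20%: 0.03 × 0.98 / (1 − 0.0006) = 0.0294 / 0.9994 = 2.94%; ratio 0.98.
- s = 50%, d = 50%: 0.03 × 0.75 / (1 − 0.0075) = 0.0225 / 0.9925 = 2.27%; ratio 0.76.

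**Increase that could be masked.** Setting the expected cohort rate to 3.0% and solving for the true rate gives 0.03 / (1 − q + 0.03q), with q = s·d. For q = 0.25 this is 0.03 / 0.7575 = 3.96%, a true ratio of 1.32.

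| s | d | Expected rate | Ratio to unselected | Expected cases in 180 (5.4 unselected) | True ratio that would read as 3.0% |
|---|---|---|---|---|---|
| 10% | 20% | 2.94% | 0.98 | 5.3 | 1.02 |
| 25% | 30% | 2.78% | 0.93 | 5.0 | 1.08 |
| 50% | 50% | 2.27% | 0.76 | 4.1 | 1.32 |
| 75% | 70% | 1.45% | 0.48 | 2.6 | 2.04 |

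The last row combines two high assumptions and marks the edge of the range; it is not an expected value.

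**Effect of the fix.** Among women enrolled before testing, s = 0, the formula returns 3.0%, and this particular bias is gone.

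**Scale of random error.** Five cases in 180 is 2.8%, with an exact 95% interval of 0.9% to 6.4%.

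**The case against.** The best case against acting has four parts.

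1. **The protocol already knows.** Section 8.7.2 names the bias and will produce defect prevalence for women enrolled before testing, and 8.2 promises descriptive information on the excluded Cohort 1 women. This stands as far as it goes. But nothing links either output to the MACDP comparison. The stratified analysis contrasts two groups inside the study, and 8.9 is silent.

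2. **The comparison is tertiary and descriptive, and table layout belongs in the Data Analysis Plan.** This limits the importance. It does not remove the point, because the protocol itself fixes which groups are set against MACDP and recognises the bias in the next section without connecting the two.

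3. **The effect may be small.** Section 8.5 expects typical exposed women to enrol early, and the late tick in Table 5 shows what is permitted, not what is common. This stands for Cohort 1, although the expectation draws on another product's registry. Random error is also likely to exceed the bias, but a confidence interval does not reveal a bias.

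4. **Other differences may offset it.** Infants are followed for up to one year, and the protocol reports that asthma itself is associated with adverse pregnancy outcomes. Either could raise the cohort rate. A reader might infer that mepolizumab will look safer than the population through selection alone; the documents do not support that. Only the direction of the entry filter is known. The net direction against MACDP is not, since its case rules and rates are not given.

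A reader might also infer from the wording of the tertiary objective that women first exposed after the first trimester dilute the rate. That does not hold: 8.3.1 defines exposure for major defects as first-trimester exposure, and Table 4 applies it to both defect denominators.

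**Conclusion.** The point holds in a limited form. The entry rules bias the cohort rates used in the MACDP comparison downward whenever some women enrol after testing and testing detects some defects. The planned remedy does not reach that comparison, and the limitations section omits the bias.

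Its size cannot be fixed from the documents. At an illustrative 3% rate, the ratio to an unselected rate is about 0.98 with 10% enrolling after a normal test and 20% of defects detected, and about 0.76 with both at 50%. Both shares are assumptions; early enrolment as expected in 8.5 would put Cohort 1 near the first figure.

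Nothing here shows the primary comparison to be wrong. That comparison would be affected only if enrolment timing relative to testing differed between Cohorts 1 and 2. The change is worth making because a known one-directional bias in a safety comparison can be removed with data already planned.

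**What to change.** In 8.7.1, present the MACDP comparison for women enrolled before prenatal testing for structural anomalies, using the stratum that 8.7.2 already defines. Show the all-enrolled rate beside it, labelled as biased downward by entry selection. Add the bias to the limitations in 8.9.

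The Annex 2 interview forms already record dates of prenatal tests and ultrasounds, so no new data are needed. The cost is one extra row per cohort and a wider interval in the smaller subset. As a rough guide, width grows with 1/√(1 − s): 1/√0.9 ≈ 1.05 times if 10% enrol after testing, and 1/√0.5 ≈ 1.41 times if half do. The loss of precision is therefore small where enrolment is as early as the protocol expects. The subset removes the entry filter only; other differences from MACDP remain and should be stated.

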### **8.3.2. Outcome definitions**

*Major Birth Defects:* a major structural defect is defined and classified using the CDC coding manual (<http://www.cdc.gov/ncbddd/birthdefects/documents/MACDPcode0807.pdf>), reported by the mother and validated through the medical record. The CDC coding manual is utilized to classify defects reported through the ongoing population-based Metropolitan Atlanta Congenital Defects Program (MACDP) and is based on agreed-upon criteria by CDC investigators for major structural defects regardless of etiology. Infant medical records are abstracted and reviewed by the study research team leaders. Final validation of the classification of all major birth defects reported in the study will be conducted by a VAMPSS Investigator with expertise in the diagnosis of birth defects.

*Preterm Delivery:* preterm delivery is defined as a spontaneous or induced delivery at <37 gestational weeks, reported by the mother and validated through the medical record. Please refer to Section 8.3.1 for further description of the method for defining gestational age and therefore preterm birth.

*Small for Gestational Age (SGA) Infants:* Live born infants who are  $\leq 10^{\text{th}}$  centile on birth weight for infant sex and gestational age will be considered small for gestational age.

The U.S. Centers for Disease Control and Prevention (NCHS) growth charts will be used for full term infants, and the Britton growth charts will be used for preterm infants (Britton et al, 1993). The outcome of birthweight is reported by the mother and validated through the medical record.

*Spontaneous Abortion:* Spontaneous abortion is defined as spontaneous pregnancy loss prior to 20 weeks' gestation. In this study, since women enrol after recognition of pregnancy, spontaneous abortions are only identified after enrollment in clinically recognized pregnancies. This outcome is reported by the mother and validated through the medical record.

*Stillbirth:* Stillbirth is defined as a fetal death that occurs >20 weeks' gestation. This outcome is reported by the mother and validated through the medical record.

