**Table 4 Denominators by Outcome**

Outcome	Denominator
Major Birth Defects Among Live Births	Pregnancies ending in live birth; with exposure in 1 st trimester for mepolizumab cohort, and other comparison groups at least one malformed infant in an individual pregnancy is considered one malformed outcome
Major Birth Defects Among All Pregnancies	Pregnancies with any outcome excluding those lost-to-follow-up; with exposure in 1 st trimester for mepolizumab cohort, and other comparison groups; at least one malformed fetuses/infants in an individual pregnancy is considered one malformed outcome
Spontaneous Abortion	Pregnancies enrolled in the study prior to 20 weeks' gestation with at least 1 follow-up data collection point after enrollment date. Exposure can occur any time in pregnancy prior to event.
Preterm Delivery	Pregnancies enrolled prior to 37 weeks gestation and ending in at least one live born infant; excluding twins or higher order multiples due to inherent higher risk of preterm birth in multiples. Exposure can occur any time in pregnancy prior to event.
Small for Gestational Age Infants	Pregnancies ending in at least one live born infant; excluding twins or higher order multiples due to the inherent higher risk of reduced birth size in multiples. Exposure can occur any time in pregnancy prior to event.
Still Birth	All pregnancies, excluding lost-to-follow-up. Exposure can occur any time in pregnancy prior to event.

Coding of outcomes is performed by the study staff using the definitions provided in the protocol. The primary source of information on exposure and outcome is the participant. Validation of study outcomes is performed using medical records. In the case of discrepancies in the two sources of report, the participant is recontacted to determine if the discrepancy can be resolved, and an SOP for adjudicating these decisions has been developed.

Missing values for the critical data for PPD studies are typically very few and nearly always less than 10%. There is generally no need to include imputation strategies; however, depending on the prevalence of missingness, sensitivity analyses will be conducted. These will be documented in the DAP.

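### Stillbirth: Kaplan-Meier is assigned to a quantity defined as the share of all followed pregnancies, which it overstates when live births are censored

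*Protocol*

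**What the plan says.** Preterm delivery, spontaneous abortion and stillbirth share one crude method in Protocol section 8.7.1 (Statistical methods), which reads: "survival methods will be used (Kaplan Meier) to estimate crude rates and confidence intervals accounting for gestational timing of enrollment in the study". For the same outcomes, a Cox model serves the adjusted comparisons, provided there are at least 20 events.

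The stillbirth quantity is set out in two places. Section 8.7.1 (Secondary Endpoints) states: "The rate of pregnancies ending in stillbirth will be compared between those in the mepolizumab-exposed group" and the two comparison cohorts. Table 4 in section 8.6.1 gives the denominator: "All pregnancies, excluding lost-to-follow-up". Section 8.3.2 fixes the window: "Stillbirth is defined as a fetal death that occurs >20 weeks' gestation".

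Elsewhere in 8.7.1 the protocol recognises four ways a pregnancy can end: "all pregnancies ending in live birth, spontaneous abortion, stillbirth or elective termination". It provides for delayed entry at enrolment. It gives no rule for pregnancies that end in one of the other ways, and names no competing-risk method. Detail is left to a Data Analysis Plan, which is not at hand.

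**The concern.** Section 8.7.1 and Table 4 together define a proportion: stillbirths over all followed pregnancies. Ordinary Kaplan-Meier recognises only the event and censoring. After 20 weeks almost every woman leaves the risk set through live birth. If those births are censored, one minus Kaplan-Meier estimates the stillbirth risk in a setting where live birth never happens, and each late stillbirth is divided by the few women still pregnant.

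The crude rate is likely to be the only stillbirth result. Twenty events need 20/800 = 2.5% stillbirth across all three cohorts, or 20/500 = 4% across the two asthma cohorts. At an assumed 0.5–2%, 800 pregnancies yield 4–16 events. The absolute rate in the exposed cohort is therefore a figure that readers will take at face value.

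**Working it through.** The protocol states no stillbirth figure, so there is nothing to reproduce. The check compares the two estimators.

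**Inputs from the protocol.** Cohorts of 200, 300 and 300; 7% preterm birth in the asthmatic comparison group (Table 3 footnote); stillbirth counted after 20 weeks.

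**Assumptions.** Stillbirth risk 0.5–2%. Preterm live births spread over weeks 28–36 with mean 34.44 weeks. Term births in weeks 37, 38, 39, 40, 41 and 42 with shares 10, 19, 34, 25, 10 and 2%, mean 39.62 weeks. The last delivery is just before 43 weeks.

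**Formulas.** With d_j events and R_j women still pregnant and under observation at time t_j:
- One minus Kaplan-Meier = 1 − Π(1 − d_j/R_j), other endings censored.
- Aalen-Johansen = Σ S(t_j−)·d_j/R_j, where S is the probability of still being pregnant.

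**Closed form, constant weekly hazard h from 20 weeks.** Mean delivery is 0.07 × 34.44 + 0.93 × 39.62 = 39.26 weeks, so mean time at risk is 19.26 weeks. The true share is close to h × 19.26. One minus Kaplan-Meier at the end is 1 − exp(−23h).

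| h per week | True share (exact) | 1 − KM | Ratio | Excess |
|---|---|---|---|---|
| 0.0003 | 0.58% | 0.69% | 1.19 | 0.11 points |
| 0.0005 | 0.96% | 1.14% | 1.19 | 0.19 points |
| 0.001 | 1.91% | 2.27% | 1.19 | 0.37 points |

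The ratio is essentially 23/19.26 = 1.19.

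**Simulation.** 3,000 runs per setting, 200 or 300 women, entry uniform over weeks 8–20. Mean ratios were 1.15–1.22; for example, at 200 women and h = 0.0005, 1.15% against 0.96%. Aalen-Johansen matched the observed proportion. A further simulation with 190 and 285 women (200 and 300 less 5% lost) gave an excess of about 17–24%.

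**Timing of stillbirths, expected weekly table, true share 1%.**

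| Timing | 1 − KM at end | Ratio | Read at 40 weeks: 1 − KM vs Aalen-Johansen |
|---|---|---|---|
| Constant hazard | 1.16% | 1.16 | 1.06% vs 0.99% (1.07) |
| Half before 28 weeks, rest even to 41 | 1.38% | 1.38 | 1.07% vs 0.96% (1.11) |
| Even over weeks 20–41 | 1.49% | 1.49 | 1.08% vs 0.95% (1.14) |

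**Instability.** One stillbirth with 10 women undelivered moves one minus Kaplan-Meier by up to 1/10 = 10 points. As a share of 200 pregnancies it is 1/200 = 0.5 points. This is uncommon: among simulated cohorts with at least one stillbirth, 2.5–3.5% had a Kaplan-Meier figure at least twice the Aalen-Johansen one.

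**Losses before 20 weeks.** Table 4 counts these pregnancies in the denominator, but Kaplan-Meier removes them before any stillbirth can occur. If, say, 10% ended that way, a 1.00% risk among pregnancies reaching 20 weeks is 0.9 × 1.00 = 0.90% of all. This comes on top of the figures above.

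**Spontaneous abortion.** Live birth plays no part here: "Spontaneous abortion is defined as spontaneous pregnancy loss prior to 20 weeks' gestation". With a true share of 10%, one minus Kaplan-Meier is 10.05% with 1% terminations, 10.25% with 5% and 10.52% with 10%, or 10.93% if those 10% all fall early.

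**The case against.** The strongest reply is that the censoring rule is inferred. No section says live births are censored, the one stated purpose of the survival method is to allow for timing of enrolment, and an analysis plan could keep pregnancies that ended otherwise in the risk set as event-free, which removes the live-birth bias. That is possible, but it is not what naming Kaplan-Meier ordinarily means. An analysis plan that follows the protocol literally inherits the problem.

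Second, sampling error is larger than the average bias: the exact 95% interval is 0.01–2.8% for 1/200 and 0.1–3.6% for 2/200. This stands and limits the practical weight of the point. It does not make the estimator target the right quantity.

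Third, reading the curve at 40 weeks cuts the excess to about 7–14%. That also stands, but the protocol fixes no reading time.

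A reader might also infer more than the documents support:
- *That spontaneous abortion is equally affected.* Only elective termination and other non-spontaneous endings compete, and the excess is negligible unless terminations are frequent. What 8.7.1 asks for there is "the rate of spontaneous abortion accounting for left truncation will be compared", which delayed-entry Kaplan-Meier addresses.
- *That stillbirth rates near 10% should be expected.* That needs a very late event with few women undelivered.
- *That the cohort comparison is materially distorted.* Much of the bias cancels if delivery timing is similar. In one check with 15% preterm and slightly earlier term births, the ratio moved only from 1.19 to 1.23.
- *That the Cox model is wrong.* A cause-specific Cox model is a legitimate choice for adjusted comparisons.

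**Conclusion.** The point holds for stillbirth. The protocol names an estimator that, in its usual form, does not estimate the share of followed pregnancies it defines, and the error is upward. The size is roughly 15–25% relative, or 0.1–0.4 percentage points, for assumed risks of 0.5–2% and typical delivery timing. It reaches about 50% if stillbirths are spread evenly to 41 weeks rather than following a constant hazard. These figures depend on assumed rates and timings and on the curve being read at the end of follow-up. They concern the absolute rate in each cohort, not an established distortion of the contrast. Stillbirth is a secondary endpoint. The primary endpoint, analysed by exact methods among live births, is untouched, and preterm delivery among live births does not share the problem.

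**What to change.** In section 8.7.1, replace Kaplan-Meier for the crude stillbirth rate with the Aalen-Johansen cumulative incidence estimator and its confidence interval, with delayed entry at enrolment and live birth, spontaneous abortion and elective termination as competing events. All three are needed because Table 4 counts every followed pregnancy. Keep the cause-specific Cox model for adjusted comparisons and Kaplan-Meier for preterm delivery. Using the same estimator for spontaneous abortion, with elective termination competing, is optional and for consistency only.

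The cost is one sentence in 8.7.1 and a matching entry in the Data Analysis Plan. Standard software does this, and no new data are needed.
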